4.3.2 Eligibility Criteria/Vulnerable Populations

Parent/Guardian Participants

To be eligible for inclusion in the study, a parent or legal guardian must meet all of the following criteria:

- Female, male or other gender ≥ 18 years of age at the time of recruitment.
- Parent or legal guardian of a child age 5 to 18 at the time of recruitment who is enrolled in school-based mental health treatment services with one of the clinician participants included in the study (see inclusion criteria for clinician participants above).
- Enrolled in school-based mental health services within 3 months prior to the recruitment date.
- English speaking.
- Ability to provide informed consent.

Parents/guardians who do not meet all inclusion criteria are excluded. There are no other exclusion criteria.

5 Study Methods/Procedures

5.1 Study Procedures

Study procedures involve collecting implementation data from clinicians (approximately N=50) as part of a district-wide measurement-based care training in initiative and recruiting parent/guardian (up to N=150) participants to provide feedback on the implementation outcomes of a pilot training and post-training consultation on measurement-based care. Study information will be provided to clinicians via email and secure, electronic survey and study consent will be provided to parents/guardians by a study team member conducting phone consent. Study procedures are built around a 3-hour professional development and monthly, post-training consultation calls that are required by participating school districts. Clinicians will also be asked to use MBC measures (e.g., Outcome Rating Scale and Session Rating Scale) with 5 students on their caseload, and completing study evaluation surveys (for which clinicians will be compensated with \$25 Amazon gift cards for each survey completed at baseline, post-training, 3-, 6-, and 9-month follow-up).

Parents/guardians of youth served by participating clinicians will be asked to consent to phone check ins (at baseline, 3-, 6-, and 9-month intervals) to report child symptoms and parent engagement. Parent/guardian participants will also be asked to consent to records

review in order for the study team to assess fidelity to MBC training and consultation. Additional study procedure details are described in the following sections.

Study Procedures vs Standard of Care

Youth (ages 5-18) who receive school-based mental health services from participating clinicians will receive measurement-based care (MBC) as part of their usual care services. MBC is aligned with best practices in psychosocial treatment delivery but is under-implemented in usual care due to numerous barriers. MBC practices, which include routine progress monitoring and feedback to inform data-driven, client-centered treatment plan adjustments, only stands to improve the quality and standard of usual care delivered to children and their families in school settings.

5.1.1 Data Collection

Data Sources. Data sourced for this study will include computerized and hard copy research records. Any hard copy research records will be scanned and saved electronically on a Yale secure server before shredding the paper copy. Data sources will include:

- (1) Quantitative data from clinician self-report surveys about **MBC acceptability, appropriateness, and feasibility** as well as **MBC use** every three months during implementation supports. Some qualitative feedback will also be solicited on the survey for clinicians to expand on any details the standardized measures of these implementation outcomes could not capture. (*Primary outcome variables*)
- (2) Quantitative data on **MBC use (clinician fidelity)** coded by chart review protocol, in which fidelity includes presence of SRS and ORS measures in the online BON/PCOMS system to approximate fidelity per clinician. (*Primary outcome variables*)
- (3) Quantitative data on proximal and distal **student engagement and functioning outcomes** collected by the clinician as part of the project, retrieved from medical records and/or the PCOMS system directly (SRS, ORS). (*Secondary outcome variables*)
- (4) Quantitative data on **parent engagement** and distal **student symptoms** collected by the study team as part of the project from parents over the phone (Therapeutic Alliance Scales, PSC-35). (*Secondary outcome variables*)
- (5) Tracking data on parent **recruitment, clinician attendance/engagement in implementation supports**. (*Implementation mechanisms*)

Data sources 1-4 above refer to primary and secondary outcomes of explicit focus in the analyses and are listed in the table below.

Table 1. List of Measures and Data Collection Methods

Outcome	Measure	Method	Reporter	Interval
MBC Acceptability (content, complexity, relative advantage)	Acceptability of Intervention Measure (AIM)	Online survey	Clinician	Pre-training 3M follow up 6M follow up 9M follow up
MBC Appropriateness (for setting, provider, students served)	Intervention Appropriateness Measure (IAM)			
Feasibility (for SMH practice)	Feasibility of Intervention Measure (FIM)			
MBC Use	Current Assessment Practice Evaluation - Revised (CAPER)			

MBC Attitudes	Attitudes toward Standardized Assessment – Monitoring and Feedback (ASA-MF)			
Implementation Determinants	MBC Feedback Form – Assess Barriers and Facilitators			Pre-training
ORS/SRS Acceptability	Usage Rating Profile – Assessment (URP-A)			3M follow up 6M follow up 9M follow up
Fidelity (MBC Use)	Retrospective coding of PCOMS measures (SRS, ORS)	Chart review and/or BON system	Study Team	Monthly
Student Engagement	Session Rating Scale (SRS)			
Student Functioning	Outcome Rating Scale (ORS)			
Student Symptoms	Pediatric Symptom Checklist (PSC-35)	Phone	Parent	Baseline* 3M follow up 6M follow up 9M follow up
Parent Engagement	Therapeutic Alliance Scales for Caregivers and Parents			

**after clinician consent, near initial clinician training*

Secure Data Recording and Maintenance:

Online survey data will be maintained in the PI's Yale Qualtrics account, accessible only by members of the study team listed on the IRB protocol. Online survey data will be downloaded and maintained on secure Yale storage servers and networks (i.e., Yale Box, network drive). Clinicians will provide their identifying information (name, email address) when they consent as well as a secure 4-digit anonymous code. They will be asked to submit this same 4-digit code with each follow-up survey. This will ensure the study team can track individual clinician responses over time, but each survey is completed confidentially. A password-protected Excel file including clinician identifying information and 4-digit codes will be maintained on secure Yale storage servers and networks, accessible only to study team members.

Chart review data may be in various formats depending on the format of documentation and storage systems at each district (study site). We only need basic information such as child diagnosis, date entered services, treatment goals, and number of sessions attended. We will also ask for their anonymous BON code so we can link those data (see below). Consistent with best practices in chart review methodology, we will work with each district to identify a "data extractor" at their site who can obtain the relevant data for students of consented parents within the requisite time frame and prepare them for the study team. Our team will provide a list of names of children based on parental consent obtained, as well as the data we are requesting. Once we receive the chart data, we will deidentify it with a unique study identifier and keep the list of linked study IDs to names in a separate password-protected file. We expect that the requested chart review material can be transferred in electronic format to our site at Yale, we will use Yale's secure file transfer system, save the material on our secure Yale storage server or network, and then complete the enter the services data for each child. These files will be saved on our secure Yale storage server and network and entered into a database.

BON/PCOMS system data (including the Outcome Rating Scale and Session Rating Scale) will be maintained in the Better Outcomes Now (www.betteroutcomesnow.com) secure online system. Clinicians enter these data directly into PCOMS using their own anonymous code for students. There are no identifiable information in PCOMS. Our study team will be the PCOMS trainers and also have administrative privileges in PCOMS to support MBC

implementation. In order to protect the confidentiality of parents consenting to the study, the study team will not share the names of consented families with clinicians in order to access their PCOMS data. Instead, we will use aggregate, deidentified PCOMS data at the clinician level to estimate MBC fidelity. This is a HIPAA-compliant site developed specifically for secure progress monitoring data entry and viewing my clinicians and their clients.

Parent-reported data collected via study phone calls will be recorded in “real time” by study team members on the Parent Survey Form either in hard copy form or electronically. All hard copy record forms will be scanned in and saved electronically on a Yale secure server before hard copy records are shredded. Parent-reported data will be entered into SPSS and saved on a Yale secure server.

The highest standards of participant confidentiality will be kept, and no participants will have identifiable information available. Computerized records of data are kept in a password-only accessible computer in a locked room. Appropriate firewalls and protections of computerized data are maintained to ensure that entry by those other than research personnel is not possible. Only study team members (the PI, her mentor, and her research assistant) will have access to individually identifiable private information about human subjects, which will only be used for tracking and follow-up purposes until data collection and compensation procedures are finalized.

5.1.2 Adverse Events Definition and Reporting

This protocol presents minimal risks to the subjects and Unanticipated Problems Involving Risks to Subjects or Others (UPIRSOs), including adverse events, are not anticipated. In the unlikely event that such events occur, Reportable Events (which are events that are serious or life-threatening and unanticipated, or anticipated but occurring with a greater frequency than expected) and/or Unanticipated Problems Involving Risks to Subjects or Others that may require a temporary or permanent interruption of study activities will be reported immediately (if possible), followed by a written report within 5 calendar days of the Principal Investigator becoming aware of the event to the IRB (using the appropriate forms from the website) and any appropriate funding and regulatory agencies. [name] will apprise fellow investigators and study personnel of all UPIRSOs and adverse events that occur during the conduct of this research project. [name] will be responsible for monitoring the data and assuring protocol compliance and safety reviews. She will conduct these reviews during her weekly supervision with research staff. Study staff will be trained to inform the PI of any adverse event or unanticipated problem in a timely fashion. [name] will evaluate whether the study should continue unchanged, require modification/amendment, or close to enrollment based on the severity of the event.

5.2 Study Schedule

Clinician involvement will require approximately 9 hours of project activities during the 2021-22 or 2022-23 school year. All activities are part of their routine services and district-approved professional development schedule. Clinician involvement includes 6 hours of training and ongoing consultation plus 2 hours and 30 minutes of online surveys.

Project activities listed on Clinician Information Sheet will include:

- **A 3-hour interactive training** on measurement-based care in schools. This training will include how to collect, score, and use student- and parent-reported progress measures with students and families to improve engagement, personalize services and inform intervention planning and adjustments throughout the school year.
- **Six, 60-minute, monthly post-training consultation calls** for six months following the training. These calls will be with other participating clinicians and the PI to facilitate peer learning and support for implementing measurement-based care in

schools. Strategies and adaptations to match the school setting and student and family strengths and needs will be discussed.

- **Four, 30-minute online feedback surveys** from clinicians to understand measurement-based care acceptability, appropriateness, and feasibility in schools, plus clinician use of measures and related experiences with implementation. These will occur before the first training and 3 months, 6 months, and 9 months after the training throughout the school year. You will receive a \$25 Amazon gift card for each survey you complete.
- **Collecting student progress data.** You will be asked to collect brief measures of student progress periodically throughout treatment, review it with the student and family and document this in an online system that we will grant you access to called Better Outcomes Now (BON). Collecting and discussing these measures will take 5-10 minutes of session time, 2-4 times per month and will be part of the regular services you already provide. We ask that you do this with at least five (5) of your students.
- **Parent recruitment.** We will ask you to refer at least five (5) parents to the research study component of this project. We will ask you to present the opportunity to participate in the study to the parents of students you work with. Parent participation is optional and will involve completing four brief phone check ins with one of our study team members during the school year. Parents will receive a \$25 Amazon gift card for each phone check in they complete. If the parent agrees to participate, the study team will also review their BON account for documentation of measures being collected and discussed. We will do this by asking you to provide our study team with their anonymous BON code so we know who the student is in BON. (As administrators, we can access all BON data, but it is deidentified). Records review in BON will occur confidentially by the study team and only if parent permission is provided.

Parent/guardian participation will require approximately 1 hour, 40 minutes of study participation during the 2021-22 or 2022-23 school year. This includes phone consent and four phone interviews of approximately 20-25 minutes each at baseline, 3 months, 6 months and 9 months.

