Study Design

A clustered, multiple-baseline design will be used to examine the impact of implementation support on clinicians' fidelity, use and ratings of MBC appropriateness, acceptability and fidelity. Approximately 50 SMH clinicians will participate from up to three school districts as a part of their regular professional development activities. In these school districts, measurement based care implementation is a district-wide quality improvement initiative. All clinicians will receive the same implementation supports; there is no random assignment to condition. Following an initial control period of at least 1 month, school districts will start receiving implementation supports. Baseline MBC use, attitudes, acceptability, feasibility and appropriateness (per clinician self-report) will be collected, as well as needs assessment data from clinician surveys to inform necessary adjustments to the implementation supports. Baseline engagement and student outcomes will be collected after initial clinician training session. MBC implementation outcomes (i.e., MBC use, attitudes, acceptability, appropriateness, and feasibility), engagement and student outcomes will be collected at 3-month and 6-month follow-up during intervention supports, plus a 9-month follow-up interval. This allows clinicians in the school districts to be compared to each other and to their own baseline. The primary comparison is pre-post ratings of implementation outcomes for all N=50 clinicians. The secondary comparisons are pre-post ratings of engagement and student outcomes, and between-agency differences.

Clinicians will receive a 3-hour professional development on MBC in Fall 2022 that is required by the three participating school districts. Monthly, post-training group consultation calls will be conducted for 6-months, and online, self-report surveys will be collected at baseline, 3-month, 6-month and 9-month intervals. Clinicians will be asked to implement measurement-based care, using the Better Outcomes Now (BON) online feedback system, with at least 5 students each. Data in BON are deidentified and this activity is part of routine care provided by clinicians, so does not require special consent. These data will also be used to inform group consultation supporting clinicians' practices.

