Implementation outcomes are selected from a published taxonomy of outcomes include acceptability, appropriateness, feasibility and fidelity. **Acceptability, appropriateness, and feasibility** will be measured by clinician self-report on the Acceptability of Intervention Measure (AIM), Intervention Appropriateness Measure (IAM), and Feasibility of Intervention Measure (FIM) via web-based, clinician-report survey. These 4-item measures were developed based on input from 36 implementation scientists and 27 mental health professionals; structural validity, test-retest reliability, and sensitivity to change have been established. **MBC use (fidelity)** will be evaluated by chart review in BON for evidence of two progress monitoring measures, the Session Rating Scale 3.0 (SRS) and Outcomes Rating Scale 3.0 (ORS). The MBC training provided as part of this study will include how to use MBC and document it in BON. The ORS will be completed before each session to assess prior-week functioning, and the SRS will be completed at the end of the session to assess student/parent perceptions of alliance with the clinician.

Secondary and Exploratory Outcome Variables

The secondary objective of this study is to examine effectiveness outcomes.

Effectiveness outcomes of MBC will be measured using actual scores on the SRS and ORS, as documented in the student's service record. The SRS and ORS are part of the Partners for Change Outcome Management System (PCOMS), a system used to enhance patient involvement in mental health services and improve therapeutic alliance and treatment progress. **Student engagement** will be measured by the SRS. **Parent engagement** will be measured by the Therapeutic Alliance Scales for Caregivers and Parents. **Symptoms and functioning** will be measured using the ORS. Emotional and behavioral symptoms will also be measured by the Pediatric Symptom Checklist, 35-item version (PSC-35) which has well-established reliability and validity to assess and monitor progress of internalizing and externalizing symptoms for children ages 4-18. The Therapeutic Alliance Scales for Caregivers and Parents and the PSC-35 will be collected directly from parents/guardians over the phone at baseline and follow-up intervals.

Study Population

This study plans to enroll up to 150 parents/legal guardians of children or adolescents receiving SMH treatment from one of the 50 participating clinicians. We anticipate SMH

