Results of all the above analyses will be expressed in terms of 95% confidence intervals for effects and contrasts which together with estimates of intra-clinician correlation and variance will inform the power analysis for a larger trial.

Mixed Methods Analyses

For (2) we will also analyze chart review data. We will develop and test our MBC fidelity rubric on a subset of consented students at midpoint in the school year to assess intercoder reliability, test our coding form on the text of progress notes, and refine both our coding form and process for accessing records in an efficient, reliable manner. These analyses will yield mixed methods data on clinician use of MBC to be triangulated with clinician self-reported use of MBC on surveys to evaluate relative advantages and disadvantages of these methods to assess use of MBC. Qualitative data generated from chart reviews will be analyzed using Rapid Qualitative Analysis whereby two coders plus the PI will create summaries of chart review findings per student using a standard summary form, which is then entered into a matrix for the entire sample to be reviewed, coded iteratively, and synthesized for main themes and sub codes. These findings will directly inform the future R01 application methods regarding the collection and use of chart review and/or clinician surveys to assess MBC use/fidelity following implementation supports.

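### The protocol does not settle whether BON-coded fidelity, a primary outcome, is built from all de-identified students or only from those with parent permission

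*Combined protocol and SAP*

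**What the plan says.** The Synopsis (Primary Outcome Variables) says that fidelity "will be evaluated by chart review in BON for evidence of two progress monitoring measures", the SRS and ORS. Section 5.1.1, item 2, lists it among the primary outcome variables and makes the clinician the unit: "fidelity includes presence of SRS and ORS measures in the online BON/PCOMS system to approximate fidelity per clinician". Neither place attaches a consent condition.

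Two student sets are then described.

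- **All de-identified students.** The BON/PCOMS paragraph of section 5.1.1, after explaining that consenting families should not be disclosed to clinicians, says: "Instead, we will use aggregate, deidentified PCOMS data at the clinician level to estimate MBC fidelity". The Synopsis (Study Design) adds: "Data in BON are deidentified and this activity is part of routine care provided by clinicians, so does not require special consent".
- **Students with parent permission.** Section 5.1 says parents are asked to consent to records "review in order for the study team to assess fidelity to MBC training and consultation". The parent-recruitment item in section 5.2 ends: "Records review in BON will occur confidentially by the study team and only if parent permission is provided". In section 5.3.1, the mixed-methods text plans to "develop and test our MBC fidelity rubric on a subset of consented students".

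On numbers, section 5.2 asks each clinician to use BON with five or more students and to refer five or more parents. Section 5.3.2 plans 50 clinicians and a ceiling of 150 parents. Sections 4.3.1 and 5.3.2 say that families are approached on the basis of the clinician's own report of which students receive MBC.

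**The concern.** The two descriptions give different samples for one primary outcome, and an analyst could follow either. Under the permission rule a clinician is seen only through families who were approached and agreed. With no such family there is nothing to code, so the clinician is missing.

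This missingness is unlikely to be unrelated to the outcome. Because approach depends on the clinician reporting MBC use, a clinician who hardly uses MBC is less likely to have a permitted family and would tend to drop out of the fidelity summary when the true value is at or near zero. The summary would then lean towards users and tend to overstate uptake of the support package. Section 5.3.6 does not cover this case: its reliance on the mixed model holds under missing at random, which is doubtful when absence depends on use.

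**Working it through.** The protocol gives no power calculation or precision target for fidelity, so there is no planned figure to reproduce. What can be checked is the size of the two student sets and how many clinicians the permission rule could lose.

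**Inputs from the documents:** 50 clinicians; at least 5 BON students per clinician (5.2); at most 150 consenting parents (5.3.2).

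**Student base**
- All BON students: 50 × 5 = 250 or more, if every clinician complies.
- Permission only: 150 or fewer, an average of 150 / 50 = 3 per clinician and at most 150 / 250 = 60% of the 250.

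**Clinicians with no permitted student, random spread.** Assume exactly five BON students per clinician and k consents falling at random over the 250 students. Then P(none) = C(245, k) / C(250, k), and the expected number is 50 × P(none). For k = 150, P(none) = (100 × 99 × 98 × 97 × 96) / (250 × 249 × 248 × 247 × 246) = 0.0096, and 50 × 0.0096 = 0.48.

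**Uneven spread.** Assume instead that consent is correlated within clinician (beta-binomial, ρ = 0.2). With p = k / 250, s = 1/ρ − 1 = 4 and b = (1 − p)s, P(none) is the product over i = 0 to 4 of (b + i) / (s + i). For k = 150, b = 1.6 and P(none) = (1.6/4)(2.6/5)(3.6/6)(4.6/7)(5.6/8) = 0.057, so 50 × 0.057 = 2.9.

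| Consents k | P(none), random | Clinicians of 50, random | Clinicians of 50, ρ = 0.2 |
|---|---|---|---|
| 150 | 0.0096 | 0.5 | 2.9 |
| 100 | 0.0757 | 3.8 | 9.2 |
| 75 | 0.1652 | 8.3 | 15.0 |
| 50 | 0.3244 | 16.2 | 23.2 |

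**Consents in blocks of five.** If consents come five per clinician, matching the referral request in 5.2, 150 consents come from 150 / 5 = 30 clinicians and 50 − 30 = 20 have none.

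The consent counts below 150, the value of ρ and the blocks of five are assumptions. All these counts also suppose that every clinician has five BON students to begin with, so they do not include clinicians lost because they did not use MBC at all.

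**The case against.** The best defence is that the plan already contains the right rule. Section 5.1.1 bases fidelity on aggregate clinician-level data. The Synopsis (Study Design) gives consented parent data a different purpose, family engagement and child outcomes. Item 2 of the revision history describes the BON identifier as a means of linking progress data to parent reports. The sentence in section 5.2 closes an item on parent recruitment and follows a remark that the team can see all BON data in de-identified form, so it can be read as covering only the review of a known student. The chart review in 5.3.1 is for testing the rubric and for triangulation.

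This shows that a split between aggregate fidelity and permitted linkage was probably intended. It does not remove the conflict. Section 5.1 names fidelity, not linkage, as the purpose of the consented review. The review in section 5.2 also looks at whether measures were discussed, which bears on the second part of Hypothesis 2 (section 3.1), a primary hypothesis. No operative section limits permission to linkage.

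Three stronger readings are tempting, and the documents do not support them.

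- A reader might infer that the primary comparison in all 50 clinicians is lost. That comparison (Synopsis, Study Design; 4.1.1) concerns clinicians' ratings, and the growth model in 5.3.1 is described for self-reported outcomes. AIM, IAM, FIM and CAPER need no parent permission.
- A reader might infer that using all BON records would breach what clinicians are told. The same item in 5.2 discloses access to all de-identified records, so that reading takes its last sentence out of context.
- A reader might infer a fixed inflation factor of 1 / (1 − p), where p is the share of clinicians without a value. That requires every unobserved clinician to be a non-user. The documents do not establish this: 5.2 asks clinicians to approach parents of students they work with, and the recruitment steps let designated site staff make the approach.

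**Conclusion.** The concern holds for BON-coded fidelity only. The sections need to be reconciled, because they define two student sets for a primary outcome and do not say what happens to a clinician with no permitted family. Following sections 5.1 and 5.2 would reduce the base from at least 250 students to at most 150 and would probably bias fidelity upwards. The direction rests on the approach rule in 4.3.1 and 5.3.2; the size of the bias cannot be derived from the documents. The number of clinicians lost could be negligible (about 0.5 of 50 with 150 consents at random) or substantial (20 of 50 with five per clinician), and it grows if fewer parents consent. Self-reported use does not fill the gap: Hypothesis 2 treats the two measures separately, and 5.3.1 plans to compare chart-review with self-reported use.

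**What to change.** 1. In the Synopsis (Primary Outcome Variables), 4.2.1 and 5.1.1 item 2, state, in line with the BON/PCOMS paragraph of 5.1.1, that primary BON fidelity is calculated for every trained clinician from all of that clinician's de-identified BON records.
2. Count active clinicians with no BON entries as zero use. Report separately those who left or had no eligible students, so that they are not counted as non-users. The result is BON-documented use; CAPER remains the source for use outside BON.
3. Reword 5.1 and 5.2 so that parent permission governs only identified, student-level review and linkage to parent-reported and services data.
4. Label the chart review in 5.3.1 as a consented-subset analysis, including any part of Hypothesis 2 that needs student-level review.
5. Reconcile the statement in 5.1.1 that consenting families' names will not be shared with clinicians to reach PCOMS data with the requests for the student's BON code in 5.1.1 and 5.2.

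The cost is an IRB amendment to the protocol and Clinician Information Sheet wording. No new data are needed, since the team already has administrator access to the de-identified records. The fidelity figure may turn out less favourable.
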